Appendix 3. Flowchart of US FDA-defined Snapshot Algorithm for Switch Trial

The following flowchart for US FDA-defined snapshot algorithm is based on the US FDA Guidance on Human Immunodeficiency Virus-1 Infection: Developing Antiretroviral Drugs for Treatment {U. S. Department of Health and Human Services 2015}

* On-treatment values include 1) data collected up to 1 day after the last dose date for subjects who prematurely discontinued or completed study drug or 2) all the data for subjects who were ongoing

Appendix 4. Cardiovascular or Cerebrovascular Events

An adverse event record will be flagged as a cardiovascular or cerebrovascular event if its MedDRA PT is included in the pre-specified PT list, which includes all PTs from the narrow search of the following 3 SMQs under MedDRA v22.0 provided by Gilead PVE (search name: Ischemic cardiac and cerebral events narrow) and reviewed by Gilead medical monitors.

	SMQ Source
Cardiovascular or Cerebrovascular Events	Ischaemic central nervous system vascular conditions (SMQ) – Narrow Scope Term
	Myocardial infarction (SMQ) - Narrow Scope Term
	Other ischaemic heart disease (SMQ) - Narrow Scope Term

Appendix 5. Hepatic Events

An adverse event record will be flagged as a hepatic event if its MedDRA PT is included in this pre-specified PT list, which includes all PTs from the broad search of the following 15 SMQs under MedDRA v22.0 provided by Gilead PVE (search name: Non-infectious, non-congenital hepatobiliary disorders) and reviewed by Gilead medical monitors.

	SMQ Source
Hepatic Events (HEP)	Biliary neoplasms benign (incl cysts and polyps) (SMQ)
	Biliary malignant tumours (SMQ)
	Biliary tumours of unspecified malignancy (SMQ)
	Biliary system related investigations, signs and symptoms (SMQ)
	Biliary tract disorders (SMQ)
	Gallbladder related disorders (SMQ)
	Gallstone related disorders (SMQ)
	Cholestasis and jaundice of hepatic origin (SMQ)
	Hepatic failure, fibrosis and cirrhosis and other liver damage-related conditions (SMQ)
	Hepatitis, non-infectious (SMQ)
	Liver neoplasms, benign (incl cysts and polyps) (SMQ)
	Liver malignant tumours (SMQ)
	Liver tumours of unspecified malignancy (SMQ)
	Liver related investigations, signs and symptoms (SMQ)
	Liver-related coagulation and bleeding disturbances (SMQ)

Appendix 6. TFL Mocks

Appendix Table 1. Subject Disposition, All Screened Subjects

Visit	GEN
Subjects Screened	75
Screen Failure Subjects Who Were Not Enrolled	15
Subjects Met All Eligibility Criteria and Not Enrolled*	5
Subjects Enrolled	55
Subjects Enrolled and Never Treated	0
Subjects in E/C/F/TAF Safety Analysis Set	55
Subjects in E/C/F/TAF Full Analysis Set	55
Subjects Completing E/C/F/TAF Study Treatment	xx (xx.x%)
Subjects Prematurely Discontinuing E/C/F/TAF Study Treatment	xx (xx.x%)
Reasons for Prematurely Discontinuing E/C/F/TAF Study Treatment	
Reason 1	xx (xx.x%)
Reason 2	xx (xx.x%)
Reason x	xx (xx.x%)
Subjects Enrolling in B/F/TAF Open Label Extension Phase	xx
Subjects in B/F/TAF Safety Analysis Set	xx
Subjects in B/F/TAF Full Analysis Set	xx
Subjects Completing B/F/TAF Study Treatment	xx (xx.x%)
Subjects Prematurely Discontinuing B/F/TAF Study Treatment	xx (xx.x%)
Reasons for Prematurely Discontinuing B/F/TAF Study Treatment	
Reason 1	xx (xx.x%)
Reason 2	xx (xx.x%)
Reason x	xx (xx.x%)
Subjects Completing Study	xx (xx.x%)
Subjects Prematurely Discontinuing from Study	xx (xx.x%)
Reasons for Prematurely Discontinuing from Study	
Reason 1	xx (xx.x%)
Reason 2	xx (xx.x%)
Reason x	xx (xx.x%)

The denominator for percentages of subjects is the number of subjects in the E/C/F/TAF Safety Analysis Set except for the categories related to the B/F/TAF Open Label Extension Phase for which the denominator is the number of subjects in the B/F/TAF Safety Analysis Set.

The number of screen failures is counted by unique subject based on the date of birth, race, ethnicity, sex, country, and initials.

* Among 5 subjects who met all eligibility criteria but were not enrolled, the reasons (N) were: withdrew consent (4) and outside of visit window (1).

Appendix Table 2. Virologic Outcome at Week 96 (HIV-1 RNA Cutoff at 50 copies/mL, Snapshot Algorithm), Full Analysis Set

	GEN (N = xxx)
HIV-1 RNA < 50 copies/mL	xx (xx.x%)
95% CI	xx.x% to xx.x%
HIV-1 RNA ≥ 50 copies/mL	xx (xx.x%)
95% CI	xx.x% to xx.x%
HIV-1 RNA ≥ 50 copies/mL in Week 96 Window	xx (xx.x%)
Discontinued Study Drug Due to Lack of Efficacy	xx (xx.x%)
Discontinued Study Drug Due to AE/Death and Last Available HIV-1 RNA ≥ 50 copies/mL	xx (xx.x%)
Discontinued Study Drug Due to Other Reasons* and Last Available HIV-1 RNA ≥ 50 copies/mL	xx (xx.x%)
No Virologic Data in Week 48 Window	xx (xx.x%)
Discontinued Study Drug Due to AE/Death and Last Available HIV-1 RNA < 50 copies/mL	xx (xx.x%)
Discontinued Study Drug Due to Other Reasons* and Last Available HIV-1 RNA < 50 copies/mL	xx (xx.x%)
Missing Data During Window but on Study Drug	xx (xx.x%)

Week 96 window is between Day 631 and 714 (inclusive).

* Other reasons include subjects who discontinued study drug due to investigator's discretion, subject decision, lost to follow up, noncompliance with study drug, protocol violation, pregnancy, and study terminated by sponsor.

Appendix Table 3. Number and Percentage of Subjects with HIV-1 RNA < 50 copies/mL by Visit, Missing Excluded

	GEN (N = xx)
HIV-1 RNA at Week XX	
< 50 copies/mL	
95% CI	
< 20 copies/mL	
< 20 copies/mL Not Detectable	
< 20 copies/mL Detectable	
20 to < 50 copies/mL	
≥ 50 copies/mL	

The denominator for percentages is the number of subjects in the E/C/F/TAF Full Analysis Set.
The 95% CI for percentage estimate of HIV 1 RNA < 50 copies/mL was obtained using Exact method.

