The percentages of subjects in the FAS with HIV-1 RNA < 50 copies/mL at Weeks 24 and 48, as determined using the US FDA-defined snapshot algorithm, were 87.3% (95% CI: 75.5% to 94.7%) and 81.8% (95% CI: 69.1% to 90.9%), respectively. The percentages of subjects with HIV-1 RNA \geq 50 copies/mL at Week 24 and Week 48 were 1.8% and 3.6%, respectively. The remaining subjects (10.9% at Week 24 and 14.5% at Week 48) had no virologic data in the corresponding window. All 6 subjects lacking virologic data in the Week 24 window and 7 of the 8 subjects lacking virologic data in the Week 48 window had prematurely discontinued study drug, with their last HIV-1 RNA value < 50 copies/mL.

The percentage of subjects in the FAS with HIV-1 RNA < 20 copies/mL at Week 48, as determined using the US FDA-defined snapshot algorithm, was 81.8% (95% CI: 69.1% to 90.9%). The percentage of subjects with HIV-1 RNA \geq 20 copies/mL at Week 48 was 3.6%. There was no virologic data in the Week 48 window for the remaining 8 (14.5%) subjects, 7 of whom had prematurely discontinued study drug with their last available HIV-1 RNA < 20 copies/mL.

At Week 48 there were no clinically significant differences between subgroups (age, sex, race, region, and study drug adherence rate) in the percentages of subjects with HIV-1 RNA < 50 copies/mL, determined using the US FDA-defined snapshot algorithm. Percentages of subjects with HIV-1 RNA < 50 copies/mL in each subgroup were generally similar to that observed in the overall study population.

When assessed using M = F and M = E imputation methods for missing data, the percentages of subjects with HIV-1 RNA < 50 copies/mL at Week 48 were 83.6% (95% CI: 71.2% to 92.2%) and 97.9% (95% CI: 88.7% to 99.9%), respectively. The percentage of subjects with HIV-1 RNA < 20 copies/mL at Week 48 was 83.6% (M = F) and 97.9% (M = E).

CD4 cell counts and CD4% remained stable through Week 48. The mean (SD) baseline CD4 cell count was 545 (239.2) cells/ μ L; the mean (SD) change from baseline at Week 48 was -16 (192.1) cells/ μ L. The mean (SD) baseline CD4% was 31.5% (9.41%); the mean (SD) change from baseline at Week 48 was 1.7% (4.10%).

Safety Results

In relation to the primary study endpoint, the incidence of treatment-emergent Grade 3 or higher AEs up to Week 48, Grade 3 or 4 AEs were reported for 32.7% of subjects (18 of 55).

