7.2.2. Analysis of Other Efficacy Endpoints

7.2.2.1. By-Visit Analysis of the Proportion of Subjects with HIV-1 RNA < 50 copies/mL by Missing Failure and Missing Excluded Approaches

The proportion of subjects with HIV-1 RNA < 50 copies/mL will be summarized using the following 2 methods for imputing missing HIV-1 RNA values:

- Missing Failure (M F)

In this approach, all missing data will be treated as HIV-1 RNA ≥ 50 copies/mL. The denominator for percentages is the number of subjects in the E/C/F/TAF FAS.

- Missing Excluded (M E)

In this approach, all missing data will be excluded in the computation of the percentages (ie, missing data points will be excluded from both the numerator and denominator in the computation). The denominator for percentages at a visit is the number of subjects in the FAS with nonmissing HIV-1 RNA value at that visit.

For both M-F and M-E analyses, the number and percentage of subjects with HIV-1 RNA in the following categories will be summarized (see [Appendix Table 3](#)):

- < 50 copies/mL
 - < 20 copies/mL
 - < 20 Not Detectable
 - < 20 Detectable
- 20 to < 50 copies/mL
- \geq 50 copies/mL

The 95% CIs of the proportion of subjects with HIV-1 RNA < 50 copies/mL will be provided using the Exact method.

Separate summaries will be provided for the E/C/F/TAF FAS and the B/F/TAF FAS.

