Appendix Table 4. Liver-Related Laboratory Test Abnormalities

	GEN (N = xx)
AST	
> 3 x ULN	xx/xx (xx.x%)
> 5 x ULN	xx/xx (xx.x%)
> 10 x ULN	xx/xx (xx.x%)
> 20 x ULN	xx/xx (xx.x%)
ALT	
> 3 x ULN	xx/xx (xx.x%)
> 5 x ULN	xx/xx (xx.x%)
> 10 x ULN	xx/xx (xx.x%)
> 20 x ULN	xx/xx (xx.x%)
AST or ALT	
> 3 x ULN	xx/xx (xx.x%)
> 5 x ULN	xx/xx (xx.x%)
> 10 x ULN	xx/xx (xx.x%)
> 20 x ULN	xx/xx (xx.x%)
Total Bilirubin	
> 1 x ULN	xx/xx (xx.x%)
> 2 x ULN	xx/xx (xx.x%)
Alkaline Phosphatase (ALP)	
> 1.5 x ULN	xx/xx (xx.x%)

	GEN (N = xx)
AST or ALT > 3 x ULN	xx/xx (xx.x%)
Total Bilirubin > 1.5 x ULN	xx/xx (xx.x%)
Total Bilirubin > 2 x ULN	xx/xx (xx.x%)
Total Bilirubin > 2 x ULN and ALP < 2 x ULN	xx/xx (xx.x%)

ULN upper limit of normal.

Denominator for percentage for individual test is the number of subjects in the E/C/F/TAF Safety Analysis Set with at least 1 postbaseline laboratory value.

The most severe postbaseline value per subject was summarized for each laboratory test. For AST, ALT, AST or ALT, and total bilirubin, subjects may be counted in multiple categories, eg, subject would be counted in > 3 ULN, > 5 ULN and > 10 ULN if the worst value was > 10 ULN.

For the composite endpoint of AST or ALT, and total bilirubin with or without alkaline phosphatase (ALP), subjects were counted once when the criteria were met at the same postbaseline visit date. The denominator is the number of subjects in the Safety Analysis set with nonmissing postbaseline values of the tests in evaluation at the same postbaseline visit date.

Appendix Table 5. Individual Data and Summary Statistics of Plasma Bictegravir Concentration (ng/mL) at Protocol-Specified Sampling Times

Subject ID	Week 4 Sparse	Week 4 Predose	Week 24 Sparse	Week 24 Predose	Week 48 Sparse	Week 48 Predose
#####-####						
#####-####						
N						
Mean						
SD						
% CV						
Median						
Min						
Max						
Q1						
Q3						
N (LN-scale)						
Geom. Mean						
95% CI(L)						
95% CI(U)						

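### The Missing = Excluded by-visit shell (SAP Appendix Table 3) states the Missing = Failure denominator, and SAP 7.2.2.1 sets no last visit for Missing = Failure

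*SAP*

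**What the plan says.** SAP 7.1 lists the by-visit proportion with HIV-1 RNA below 50 copies/mL among the secondary efficacy endpoints for the final analysis. SAP 7.2.2.1 gives two ways to handle missing values.

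- **M=F:** "all missing data will be treated as HIV-1 RNA ≥ 50 copies/mL", with all E/C/F/TAF FAS subjects in the denominator.
- **M=E:** missing values leave both numerator and denominator. "The denominator for percentages at a visit is the number of subjects in the FAS with nonmissing HIV-1 RNA value at that visit".

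One shell is cited for both: "For both M-F and M-E analyses, the number and percentage of subjects with HIV-1 RNA in the following categories will be summarized", with a pointer to Appendix Table 3. The section asks for separate summaries for the E/C/F/TAF FAS and the B/F/TAF FAS, but the M=F sentence names only the E/C/F/TAF FAS.

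Appendix Table 3 is titled "Number and Percentage of Subjects with HIV-1 RNA < 50 copies/mL by Visit, Missing Excluded". Its footnote reads "The denominator for percentages is the number of subjects in the E/C/F/TAF Full Analysis Set".

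On timing, neither 7.1 nor 7.2.2.1 names a last visit, and the shell shows only a generic week. The HIV-1 RNA analysis windows run to Weeks 108 and 120 in the E/C/F/TAF phase (Table 3-1) and to Week 60 in the extension (Table 3-7).

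**The concern.** The title and footnote of Appendix Table 3 cannot both be followed. A programmer working from the shell would divide by everyone in the E/C/F/TAF FAS, missing or not, under a title that says missing values are excluded. The M=E percentage would collapse onto the M=F percentage, and the categories would no longer add to 100%.

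This matters a little more for the extension. The snapshot analysis in SAP 7.2.1 is specified for the E/C/F/TAF FAS only, so these by-visit tables are the HIV-1 RNA response summary that the SAP specifies for B/F/TAF. Neither the M=F sentence nor the shell footnote names the B/F/TAF FAS.

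The second matter is conditional. M=F over a full analysis set makes sense while every subject is still due a sample. Beyond that, a subject who finished or switched as planned and has no sample in the window would be counted as having HIV-1 RNA of 50 copies/mL or more.

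**Working it through.** **Inputs**

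- E/C/F/TAF FAS: 55 subjects (SAP Appendix Table 1).
- Week 48 results in Protocol 1.2.5, introduced by "When assessed using M = F and M = E imputation methods for missing data": M=F 83.6% (95% CI 71.2 to 92.2) and M=E 97.9% (88.7 to 99.9).
- Interval method: exact, two-sided 95% (SAP 7.2.2.1), computed as Clopper-Pearson.

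**Step 1. Reproduce the reported figures.**

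- M=F: 46/55 = 83.6%, exact CI 71.2 to 92.2. This matches.
- M=E: among all fractions x/n with n from 30 to 55, only 46/47 gives 97.9% with limits 88.7 and 99.9. The nearest alternative, 47/48, also rounds to 97.9% but has a lower limit of 88.9.

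So at Week 48, 47 subjects had a value, 46 of them below 50 copies/mL and 1 not, and 55 − 47 = 8 had no value. The reported analysis used the denominators defined in 7.2.2.1.

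**Step 2. Apply the shell's footnote to the same data.**

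| Row | M=E as in 7.2.2.1 | M=E as in the shell footnote | M=F as in 7.2.2.1 |
|---|---|---|---|
| Below 50 | 46/47 = 97.9% | 46/55 = 83.6% | 46/55 = 83.6% |
| 50 or more | 1/47 = 2.1% | 1/55 = 1.8% | (1 + 8)/55 = 16.4% |
| Total | 100% | 47/55 = 85.5% | 100% |

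The response falls by 97.87 − 83.64 = 14.2 points, and its CI becomes 71.2 to 92.2. The remaining 8/55 = 14.5% sit in no row.

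**Step 3. Compare with neighbouring shells.** Where Appendix Table 4 needs an observed-data denominator, its footnote says so: "Denominator for percentage for individual test is the number of subjects in the E/C/F/TAF Safety Analysis Set with at least 1 postbaseline laboratory value". Appendix Table 2, a Week 96 shell, still carries the row label "No Virologic Data in Week 48 Window". That suggests text carried over from other shells, though it does not prove how the Appendix Table 3 footnote arose.

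**Step 4. Late visits under M=F.** The windows are Days 715 to 798 (Week 108), Days 799 to 882 (Week 120) and, in the extension, Days 379 to 462 (Week 60). Two groups may have no E/C/F/TAF-phase value after Week 96: subjects who stop at Week 96 without entering the extension (SAP 1.2), and subjects who switch, whose E/C/F/TAF-phase data end at the first B/F/TAF dose (SAP 3). With m such subjects at a visit, the M=F percentage is lower by m/55, so 1/55 = 1.8 points each. The documents do not give m. They also do not give the size of the B/F/TAF FAS, so the cost per subject in that table cannot be stated.

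**The case against.** The best defence is that this is a shell error the SAP already resolves. Section 7.2.2.1 defines both denominators clearly, one shell serves both methods, and the Week 48 analysis was done correctly. The 14.2 points arise only if a programmer follows the footnote over the text and nobody notices rows that fail to sum. That argument keeps the point minor, and it shows which denominator was meant. It does not remove the conflict, because the one shell printed is the M=E version and its footnote is wrong for M=E.

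On late visits, the defence is that the SAP never says rows for Weeks 108, 120 or 60 OL will be produced. A window alone does not show it: the VAS shares Table 3-1, yet SAP 10 has that questionnaire assessed only through Week 96. M=F counts missing as failure by definition, and the paired M=E table would let a reader see the cause of a drop. This stands, so the second point is a request for clarification.

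Nor does everyone stop at one date. US subjects may continue E/C/F/TAF with visits every 12 weeks (SAP 1.2). Protocol 6.4.2 provides for subjects who reach the End of E/C/F/TAF Visit and then do not roll over. Extension visits run for at least 48 weeks, although Protocol 3.3 lists them only to Week 48 OL. Some late samples will therefore be legitimate and scheduled.

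A reader might infer more than the documents support:

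- **That the Week 48 M=E result was miscalculated.** It was not; 46/47 reproduces it.
- **That the final analysis will count planned completers as virologic failures.** The SAP does not commit to those rows.
- **That the main results are at risk.** The primary endpoint is an adverse event incidence, and the Week 96 snapshot has its own category for subjects without data.

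**Conclusion.** The Appendix Table 3 footnote is wrong as written for a table titled Missing Excluded. Severity is minor: this is a descriptive reporting error, though in an analysis listed as a secondary efficacy endpoint. Followed literally on the Week 48 data, it would turn 97.9% into 83.6% and leave 8 of 55 subjects unclassified. That size rests on the reconstruction 46/47 and 46/55, which matches the published estimates and intervals. The size at other visits depends on how many values are missing there.

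The missing last visit for M=F is a secondary, conditional point. It has an effect only if the later rows are tabulated and planned completers or switchers lack samples in those windows. The number affected cannot be determined from the documents.

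**What to change.** 1. In Appendix Table 3, change the M=E footnote so that the denominator is subjects in the respective FAS with nonmissing HIV-1 RNA at that visit.
2. Give the M=F version its own footnote naming the respective FAS.
3. In SAP 7.2.2.1, amend the M=F denominator to the respective FAS (E/C/F/TAF or B/F/TAF). Without this, the corrected M=F footnote would disagree with the text for the extension table.
4. Add to 7.2.2.1 that M=F is reported only through Week 96 (E/C/F/TAF) and Week 48 OL (B/F/TAF), the last visits planned for all subjects in each phase, with M=E alone at any later visit.

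The cost is two footnotes, one amended sentence and one new sentence, with no new data. SAP 1 provides for changes after finalization to be documented in the final clinical study report, so this can still be done if the SAP is closed. The downside is that there would be no all-subject M=F estimate after those visits. The Week 48 row label in Appendix Table 2 can be corrected at the same time.

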Appendix Table 4. Liver-Related Laboratory Test Abnormalities

	GEN (N = xx)
AST	
> 3 x ULN	xx/xx (xx.x%)
> 5 x ULN	xx/xx (xx.x%)
> 10 x ULN	xx/xx (xx.x%)
> 20 x ULN	xx/xx (xx.x%)
ALT	
> 3 x ULN	xx/xx (xx.x%)
> 5 x ULN	xx/xx (xx.x%)
> 10 x ULN	xx/xx (xx.x%)
> 20 x ULN	xx/xx (xx.x%)
AST or ALT	
> 3 x ULN	xx/xx (xx.x%)
> 5 x ULN	xx/xx (xx.x%)
> 10 x ULN	xx/xx (xx.x%)
> 20 x ULN	xx/xx (xx.x%)
Total Bilirubin	
> 1 x ULN	xx/xx (xx.x%)
> 2 x ULN	xx/xx (xx.x%)
Alkaline Phosphatase (ALP)	
> 1.5 x ULN	xx/xx (xx.x%)

	GEN (N = xx)
AST or ALT > 3 x ULN	xx/xx (xx.x%)
Total Bilirubin > 1.5 x ULN	xx/xx (xx.x%)
Total Bilirubin > 2 x ULN	xx/xx (xx.x%)
Total Bilirubin > 2 x ULN and ALP < 2 x ULN	xx/xx (xx.x%)

ULN upper limit of normal.

Denominator for percentage for individual test is the number of subjects in the E/C/F/TAF Safety Analysis Set with at least 1 postbaseline laboratory value.

The most severe postbaseline value per subject was summarized for each laboratory test. For AST, ALT, AST or ALT, and total bilirubin, subjects may be counted in multiple categories, eg, subject would be counted in > 3 ULN, > 5 ULN and > 10 ULN if the worst value was > 10 ULN.

For the composite endpoint of AST or ALT, and total bilirubin with or without alkaline phosphatase (ALP), subjects were counted once when the criteria were met at the same postbaseline visit date. The denominator is the number of subjects in the Safety Analysis set with nonmissing postbaseline values of the tests in evaluation at the same postbaseline visit date.

Appendix Table 5. Individual Data and Summary Statistics of Plasma Bictegravir Concentration (ng/mL) at Protocol-Specified Sampling Times

Subject ID	Week 4 Sparse	Week 4 Predose	Week 24 Sparse	Week 24 Predose	Week 48 Sparse	Week 48 Predose
#####-####						
#####-####						
N						
Mean						
SD						
% CV						
Median						
Min						
Max						
Q1						
Q3						
N (LN-scale)						
Geom. Mean						
95% CI(L)						
95% CI(U)						
# BLQ						

BLQ Below Limit of Quantitation.

Geom. Mean Geometric Mean. LN Natural log.

PPD

Appendix 7. Programming Specifications

1) AGE is calculated as follows:

- a) AGE (years) is calculated from the number of days between the date of birth (DOB) and Day 1 (first E/C/F/TAF dose date),
- b) Use the SAS INTCK function to determine the number of “1st-of-month days” (eg, January 1st, February 1st, March 1st) between DOB and Day 1 (inclusive),
- c) Divide the result in (b) by 12,
- d) AGE – the integer of the result in (c),
- e) If the DOB and Day 1 have the month in common and the birthday is later in the month than the date of Study Day 1, then subtract one from the AGE result above.

For subjects enrolled and never dosed with study drug, age will be calculated from the date of enrollment.

Age for laboratory test reference range will be based on the age at the sample collection date.

- 2) All screened subjects refer to all subjects who are screened and have a screening number. For summarization, same subject is counted only once. DOB and other demographic information such as sex, race, ethnicity, country, and initials will be used for identifying unique screened subjects.
- 3) Screen failure subjects are the subjects who were screened and answered “No” for any inclusion criteria or “Yes” for any exclusion criteria regardless of which version of protocol the subject was consent to.
- 4) Subjects in the All Enrolled analysis set are defined as subjects enrolled into the study. IXRSENRL is the source to determine whether the subject is enrolled.
- 5) In disposition table, the reasons for premature discontinuation are displayed in the order as they appear on the eCRF.
- 6) Body mass index (BMI) is calculated from height in meters (eg, height in cm/100) and weight in kilograms as:
 - BMI will be calculated at baseline. Baseline height and weight will be used for the Calculation: Height will be obtained from *Vital Signs Performed eCRF* at screening visit; Weight will be obtained from *Vital Signs Performed eCRF* at the baseline visit; if it is missing, Weight at the screening visit from *Vital Signs Performed eCRF* will be used. For B/F/TAF baseline, the last nonmissing Weight value obtained on or prior to the date of first B/F/TAF study drug will be used.

BMI (weight [kg]) / (height [meters]²)

7) Please note, “Not Permitted”, “Unknown”, or missing categories will be excluded for percentage calculation. Except for Mode of infection (HIV Risk Factors), where “Unknown” will be included for percentage calculation, since a subject may fit more than 1 HIV risk factors, therefore percentage may add to more than 100%.

Subjects with Race “Not Permitted” will also be excluded to define Race subgroup (ie, black vs. nonblack) for efficacy subgroup analysis.

8) Baseline disease characteristics

Baseline disease characteristics in Section 5.2 will be summarized for both the E/C/F/TAF Safety Analysis Set and the B/F/TAF Safety Analysis Set. Baseline disease characteristics collected at enrollment include mode of infection, HIV disease status, HCV antibody status, medical history (including Type I or II diabetes, cardiovascular disease, hypertension, hyperlipidemia), smoking status, duration of hemodialysis, and pre-switch ARVs. These characteristics are defined prior to the first dose of E/C/F/TAF.

The following baseline characteristics will be re-defined for the B/F/TAF summary:

- HIV-1 RNA categories (copies/mL): (a) < 50 and (b) ≥ 50
- CD4 cell count (/µL)
- CD4 cell count categories (/µL): (a) < 50, (b) ≥ 50 to < 200, (c) ≥ 200 to < 350, (d) ≥ 350 to < 500, and (e) ≥ 500
- CD4%
- eGFR_{CG} (mL/min)

9) Medical history of interest at study entry

Medical history of diabetes, hypertension, cardiovascular disease, and hyperlipidemia will be summarized at study entry (E/C/F/TAF baseline) as baseline disease characteristics. A subject who had medical history of one of these diseases is a subject who experienced at least one selected medical history reported in the Medical History eCRF, including keywords as below.

Hypertension	Diabetes	Cardiovascular Disease	Hyperlipidemia
HYPERTENSION	DIABETES	CEREBRAL VASCULAR ACCIDENT	HYPERLIPIDEMIA
HIGH BLOOD PRESSURE	DIABETIC	CEREBROVASCULAR ACCIDENT	DYSLIPIDEMIA
		MYOCARDIAL INFARCTION	HYPERCHOLESTEREMIA
		CONGESTIVE HEART FAILURE	HYPERCHOLESTOLEMIA
		CORONARY ARTERY DISEASE	HIGH CHOLESTEROL
		CORONARY ARTERY CALCIFICATION	HIGH TRIGLYCERIDES
		PERIPHERAL VASCULAR DISEASE	ELEVATED CHOLESTEROL
		CARDIOMYOPATHY	HYPERGLYCEMIA
		HEART DISEASE	
		TRANSIENT ESCHIMIC ATTACK	
		AGINA	
		ARTERY BLOCKAGE	
		CARDIOVASCULAR DISEASE	

In addition, subject who experienced hypertension before starting study drug according to Adverse Event eCRF with reported term includes the key word “HYPERTENSION”.

10) To calculate years on hemodialysis at study entry, please use the Medical History CRF to find the earliest (according to MH start date on Medical History CRF) hemodialysis medical record containing any of the following keywords:

- “ESRD”
- “END” + “STAGE” + “RENAL”/“KIDNEY” + “DISEASE”/“FAILURE”
- “RENAL”/“KIDNEY”/“HEMO” + “DIALYSIS”
- “RENAL”/“KIDNEY” + “DISEASE”/“FAILURE” + “SEVERE”/“STAGE_VI”

For each subject, year on HD = year of first E/C/F/TAF dose date - start year of the hemodialysis medical record captured as above + 1.

11) Smoking status at study entry

Smoking status at baseline (ie, never smoked, former smoker, and current smoker) will be summarized as part of the baseline disease characteristics.

Former smoker at baseline refers to the subjects who have stopped the use of any Cigarettes or Cigars before study day 1 (ie, the first E/C/F/TAF dose date).

Current Smoker at baseline refers to the smokers who have used any Cigarettes or Cigars at study day 1.

Never smoker at baseline refers to subjects who have no record with Type of Substance Use “Cigarettes” or “Cigars” on or prior to study day 1.

How to classify a subject as never smoker, former smoker, or current smoker at baseline is specified as follows:

- a) First select only records with *Type of Substance Use* “Cigarettes” or “Cigars”. Records with *Type of Substance Use* “Other” (including chew tobacco, e-cigarettes, etc) will not be considered as smoking.
- b) Second, for each selected substance use record, flag whether it is “Prior”, “Present”, or “Post” relative to the first E/C/F/TAF dose date according to the algorithm below.
- c) Finally, (1) the subject will be flagged as “Never” smoker, if the subject has no record with *Type of Substance Use* “Cigarettes” or “Cigars” or all selected records have a flag of “Post”; (2) the subject will be flagged as a “Former” smoker, if any selected record has flag of “Prior” and no record of “Present”; (3) Otherwise, the subject will be flagged as a “Current” smoker, if any selected records has a flag of “Present”.

	Selected Substance Use Records							
Prior	No	No	Yes	Yes	Yes	No	No	Yes
Present	No	No	No	No	Yes	Yes	Yes	Yes
Post	No	Yes	No	Yes	No	No	Yes	Yes
Smoking Status	Never	Never	Former	Former	Current	Current	Current	Current

Algorithm to flag whether a selected record is “Prior”, “Present”, or “Post” relative to the first E/C/F/TAF dose date:

- a) The start and stop dates of the selected record are not completely missing (ie, at least year is known) or the start date is not missing and record is ongoing. The complete start or stop dates will be used to compare with the first dose date whenever possible. Otherwise, the month and year (or year alone if month is not recorded) of the start or stop dates will be used to compare with the first dose date when the start or stop date of the selected record is incomplete:
 - i) The record is flagged as “Prior”, if the stop date is before the first dose date;
 - ii) The record is flagged as “Present”, if the start date is on or before the first dose date and the stop date is on or after the first dose date, or the selected record is marked as ongoing and the start date is on or before the first dose date;
 - iii) The record is flagged as “Post”, if the start date is after the first dose date
- b) The start date of the selected record is completely missing. We assume that the start date is before the first dose date, the stop date (or the month and/or year of the stop date, if stop date is incomplete) or “ongoing” will be used to determine whether the selected record is “Prior” or “Present” as follows:
 - i) The record is flagged as “Prior”, if the stop date is before the first dose date or the stop date is completely missing and the record is not marked as ongoing.
 - ii) The record is flagged as “Present”, if the stop date is on or after the first dose date or the selected record is marked as ongoing.
- c) The start date of the selected record is before the first dose date, but the stop date is completely missing and the record is not marked as ongoing. We assume that the end date is before the first dose date, the record is flagged as “Prior”.
- d) The start date of the selected record is on or after the first dose date, but the stop date is completely missing and the record is not marked as ongoing. This is a data issue, should be queried first. However, this record is flagged as “Present” if the start date is on the first dose; this record is flagged as “Post” if the start date is after the first dose.

12) Clarification for defining Pre-ARV Categories.

Subjects are grouped by the pre-ARV at baseline (pre-switch). Pre-switch ARVs include ARVs that the subject was receiving 1 or 2 days before the first dose date. For each subject, classify them in each ARV category per [Appendix Table 6](#).

